Approximately 416 participants will be enrolled into the Main Cohort (Cohort A) and randomized to one of 3 doses of ponsegromab (100 mg [n=18], 200 mg [n=18], or 300 mg [n=190]) or to matched placebo (n=190). Participant randomization will be stratified based on CCI [REDACTED] KCCQ-23 CSS: <45 or ≥45. Approximately 195 additional participants may be enrolled into optional Cohort C and randomized in a 2:1 ratio to either 100 mg ponsegromab (n~130) or to matched placebo (n~65). The additional participants in optional Cohort C will allow for a more comprehensive evaluation of the safety and efficacy of the ponsegromab 100 mg dose level compared to placebo. For each of these cohorts, blinded study drug will be administered SC Q4W for a total of 6 doses during the 22-week treatment period.

The primary endpoint for the study is the change from baseline at Week 22 in KCCQ-23 CSS, an HRQL PRO instrument. CCI [REDACTED]

Approximately 100 participants (maximum of approximately 150) who meet all eligibility criteria for Cohorts A and C, except the requirement for serum GDF-15 concentration CCI pg/mL, may be enrolled into the optional Cohort D and randomized in a 1:1 ratio to either 300 mg ponsegromab (n~50) or to matched placebo (n~50), administered SC Q4W for a total of 6 doses during the 22-week treatment period. Participant randomization in Cohort D will be stratified by KCCQ-23 CSS: <45 or ≥45. The purpose of this optional cohort is for a supportive assessment of efficacy and safety endpoints across the spectrum of GDF-15 concentrations in participants with HF.

This study will use an unblinded E-DMC to monitor the safety of participants and an unblinded IRC to monitor the efficacy and safety of participants. A blinded Steering Committee will monitor the proportion of study participants with various NYHA classes, left ventricular ejection fractions, GDF-15 concentrations, KCCQ-23 CSS scores, and the relative proportions qualifying under the cachexia, fatigue, and functional impairment criteria and may cap 1 or more to ensure a broad population.

This study will also use a separate blinded adjudication committee consisting of independent external experts who will be responsible for adjudication of all deaths and investigator-reported HF hospitalizations and urgent HF visits.

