- a. A total of 6 doses will be administered from Day 1 to Week 20.
- b. As different volumes are required for the different dose levels of ponsegromab, each study arm will have a volume-matched placebo to maintain blinding within each study arm. Each dose will be administered as 2 SC injections of equal volume. In addition, during SV2 all participants will receive 2 SC injections of open-label placebo (equivalent to high dose, 300 mg) to assess injection tolerability.

	Study Arms for Open-label, PK Cohort (Cohort B) ^{a,b}		
Arm Title	Ponsegromab 100 mg	Ponsegromab 200 mg	Ponsegromab 300 mg
Arm Type	Experimental n=4	Experimental n=8	Experimental n=8
Arm Description	Participants will receive 100 mg Q4W SC	Participants will receive 200 mg Q4W SC	Participants will receive 300 mg Q4W SC
Associated Intervention Labels	Ponsegromab 100 mg	Ponsegromab 200 mg	Ponsegromab 300 mg

- a. A total of 4 doses will be administered from Day 1 to Week 12.
- b. If not previously administered, participants will receive 2 SC injections of open-label placebo (equivalent of highest possible dose, 300 mg) during the screening period to assess injection tolerability.

	Study Arms for Cohort C ^a	
Arm Title	Ponsegromab or Placebo^b 100 mg	
Arm Type	Experimental n~130	Placebo n~65
Arm Description	Participants will receive 100 mg Q4W SC	Participants will receive placebo Q4W SC
Associated Intervention Labels	Ponsegromab 100 mg	Placebo

- a. A total of 6 doses may be administered from Day 1 to Week 20.
- b. Each dose will be administered as 2 SC injections of equal volume. In addition, during SV2, all participants will receive 2 SC injections of open-label placebo (equivalent of highest possible dose, 300 mg) to assess injection tolerability.

	Study Arms for Cohort D ^a	
Arm Title	Ponsegromab or Placebo^b 300 mg	
Arm Type	Experimental n~50	Placebo n~50
Arm Description	Participants will receive 300 mg Q4W SC	Participants will receive placebo Q4W SC
Associated Intervention Labels	Ponsegromab 300 mg	Placebo

- a. A total of 6 doses may be administered from Day 1 to Week 20.
- b. Each dose will be administered as 2 SC injections of equal volume. In addition, during SV2, all participants will receive 2 SC injections of open-label placebo (equivalent of highest possible dose, 300 mg) to assess injection tolerability.

Ethical Considerations:

[figure not shown]

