The results of previous studies of ponsegromab support the investigation of its use for improving symptoms of heart failure, and there is a favorable benefit-risk profile to support the rationale for this study. Taking into account the measures to minimize risk to participants,

the potential risks associated with ponsegromab are justified by the anticipated benefits that may be afforded to participants with heart failure.

[figure not shown]
- Participants may benefit, clinically, from more intense monitoring and more frequent assessments compared to usual standard of care. Participants may benefit from contributing to research in heart failure and improving our understanding of the condition.
- Based on the experience with ponsegromab, the potential risks for its use in heart failure include discomfort from subcutaneous injections and/or injection site reactions.
- Participants will be expected to commit time and may experience some discomfort while undergoing study assessments. In addition, participants of childbearing potential must agree to use appropriate contraception methods.

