6.2.1. Preparation and Dispensing

Investigational Product, ponsegromab (100 mg/mL) and placebo will be prepared in a blinded fashion by qualified personnel according to the IP manual. The study intervention will be administered in a blinded fashion by qualified personnel to the participants. A second staff member will verify the dispensing.

Open-label, PK cohort (Cohort B) only: Open-label ponsegromab will be prepared as per treatment assignment by qualified personnel according to the IPM, and administered by qualified personnel to the participants. A second staff member will verify the dispensing.

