9.5. Sample Size Determination

The planned total sample size for the study is up to approximately 781 randomized participants.

Main Cohort (Cohort A)

A sufficient number of participants will be screened to achieve a total of approximately 416 randomized participants, with 380 participants randomly assigned to ponsegromab 300 mg Q4W and placebo Q4W in approximately a 1:1 ratio, plus an additional 36 participants randomly assigned to ponsegromab 100 mg Q4W and 200 mg Q4W in approximately a 1:1 ratio. Participants will be randomized initially in a 1:1:1:1 ratio to all four treatment arms (until approximately 72 participants are randomized), followed by a 1:1 ratio to the 300 mg Q4W and placebo arms only. This planned number of randomized participants is expected to ensure completion of the Main Cohort (Cohort A) of approximately 161 evaluable participants in the 300 mg Q4W and placebo Q4W treatment arms and approximately 15 evaluable participants in the 100 mg and 200 mg Q4W treatment arms, assuming a discontinuation rate of 15% (if this rate is higher, or there is a high rate of non-compliance, more participants may be randomized to ensure the required number of evaluable participants).

The sample size in the ponsegromab 300 mg Q4W and placebo arms is based

CCI

CCI

The sample size in the ponsegromab 100 mg and 200 mg Q4W arms has been chosen empirically to provide sufficient data to gain a preliminary understanding of the PK/PD relationship in this population, and is not based on the primary endpoint.

Open-Label, PK Cohort (Cohort B)

Approximately 20 additional participants will be randomly assigned to open-label ponsegromab 100 mg, 200 mg and 300 mg Q4W in approximately a 1:2:2 ratio. This sample size has been chosen empirically to provide sufficient evaluable participants (approximately 15) to adequately evaluate the PK of ponsegromab following repeated SC administration to participants with HF and elevated circulating GDF-15 concentrations, assuming a 15% discontinuation rate (if this rate is higher, or there is a high rate of non-compliance, more participants may be randomized to ensure the required number of evaluable participants).

Cohort C (optional)

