## 5.2. General Methods

*Following PCD, the data will be analyzed and reported in a CSR. The results for the open-label, PK cohort (Cohort B) may be reported in a separate CSR.*

*For safety analyses and PK/PD/immunogenicity analyses, the Main Cohort (Cohort A) and Cohort C will be reported combined, with data from the same treatment group combined across cohorts; the open-label, PK cohort (Cohort B) will be reported separately; Cohort D will be reported separately.*

Efficacy analyses will be produced using 4 different approaches:

1. Main Cohort (Cohort A) only: The main efficacy analyses for the 300 mg ponesegromab treatment group will be performed using data from the Main Cohort (Cohort A) only; statistical models will include data from the 300 mg ponesegromab treatment group and placebo only. Summaries will include data from all treatment groups.
2. The open-label, PK cohort (Cohort B) only: The open-label, PK cohort (Cohort B) will be presented separately from the Main Cohort (Cohort A), Cohort C and Cohort D.
3. Main Cohort (Cohort A) and Cohort C combined: The main statistical analyses for the 100 mg and 200 mg ponesegromab treatment groups will be performed using combined data from the Main Cohort (Cohort A) and Cohort C; statistical models will include data from all three ponesegromab treatment groups and placebo, with these analyses also providing sensitivity analyses for the 300 mg ponesegromab treatment group. Summaries will include data from all treatment groups. Data from the same treatment group will be combined across cohorts, and cohort will be added as a term in the statistical models.
4. Main Cohort (Cohort A) and Cohort D combined: These analyses will provide sensitivity analyses for the 300 mg ponesegromab treatment group, in participants with any serum GDF-15 concentration. Both summaries and statistical models will include data from the 300 mg ponesegromab treatment group and placebo only. Data from the same treatment group will be combined across cohorts, and cohort will be added as a term in the statistical models.

The analyses related to the primary, secondary and exploratory endpoints will be based on the appropriate population for analysis (see Section 4).

Unless otherwise stated, all summaries and plots will be presented by treatment group. The following treatment group labels (or similar) will be used:

DMB02-GSOP-RF02 7.0 Statistical Analysis Plan Template 31-Jan-2022

PFIZER CONFIDENTIAL

TMF Doc ID: 98.03

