It should be recognized that most studies are not designed to reliably demonstrate a causal relationship between the use of a pharmaceutical product and an adverse event or a group of adverse events. Except for select events in unique situations, studies do not employ formal adjudication procedures for the purpose of event classification. As such, safety analysis is generally considered as an exploratory analysis and its purpose is to generate hypotheses for further investigation. The 3-tier approach facilitates this exploratory analysis.

TEAE classed as Tier 1 events (except for the PK cohort) will be tabulated by treatment group. The number and percentage of participants, reporting events listed in the pre-specified Tier 1 list, will be tabulated by treatment group (with ponesegromab treatment groups combined only) and overall, and by severity. Note that Tier 1 events are not planned to be presented graphically due to the small number of expected events.

Note that Tier 1 and 2 events will not be presented for the open-label, PK cohort (Cohort B).

Injection site reactions (ISR) will also be summarized by treatment group (including ponesegromab combined) and overall, in accordance with sponsor reporting standards. The ISRs will be sorted in descending frequency within a system organ class. Incidence and severity of ISR tables will additionally be produced ('All causality' and 'Treatment related', separately) to summarise the total number of ISR by preferred term, which will be reported by treatment group (including ponesegromab combined) and overall.

Potential immunogenic AEs will be summarized by medical evaluation category (see Section 3.2.5.1) and treatment groups (including ponesegromab combined) and overall.

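### The pooled placebo group in the Cohort A + C injection site reaction tables mixes three injection volumes, so the 100 mg rate is read mainly against larger-volume placebo

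*SAP*

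**What the plan says.** The Protocol synopsis (study arms, footnote b) explains why there are several placebos: "As different volumes are required for the different dose levels of ponsegromab, each study arm will have a volume-matched placebo to maintain blinding". The number of injections does not vary: "Each dose will be administered as 2 SC injections of equal volume". The strength is fixed (Protocol 6.2.1: "Investigational Product, ponsegromab (100 mg/mL) and placebo will be prepared in a blinded fashion"), so the total volume rises with dose. Under Protocol 6.4, the blind covers drug against placebo within a dose level.

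The Protocol arm tables give the Cohort A placebo as 6, 6 and 178 at the 100, 200 and 300 mg volumes. In Cohort C, participants are "randomized in a 2:1 ratio to either 100 mg ponsegromab (n~130) or to matched placebo (n~65"), all at the 100 mg volume.

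SAP 5.2 reports Cohorts A and C together for safety, "with data from the same treatment group combined across cohorts", and lists a single placebo label beside the three dose labels. SAP 6.2.5.1 applies these groups to ISRs: "Injection site reactions (ISR) will also be summarized by treatment group (including ponesegromab combined) and overall, in accordance with sponsor reporting standards". No SAP output splits placebo by volume. SAP 6.2.5.1 plans a risk difference with a 95% interval for each dose against placebo only for Tier 2 terms. Under SAP 3.2.5.1 these are terms that are not Tier 1 and are reported by at least 5% of placebo or of combined ponsegromab participants.

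**The concern.** Injected volume is a plausible cause of local reactions in its own right. For most safety endpoints the three placebos are interchangeable; for ISRs they may not be. The design randomises a comparator with the same volume as each dose, and the ISR tables do not use it.

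This matters because local tolerability is a risk that the Protocol names: "the potential risks for its use in heart failure include discomfort from subcutaneous injections and/or injection site reactions". Cohort C was added for a fuller evaluation of the safety and efficacy of 100 mg, and 100 mg is a dose for which most of the pooled placebo has another volume. The 100 mg and placebo columns will be read side by side as a drug effect even though the table is descriptive.

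**Working it through.** **Inputs.** Strength 100 mg/mL (Protocol 6.2.1); two injections per dose (synopsis, footnote b); placebo 6/6/178 in Cohort A and about 65 in Cohort C (arm tables); active 18/18/190 in Cohort A and about 130 at 100 mg in Cohort C.

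**Volumes (derived, not printed in the documents).** 100, 200 and 300 mg at 100 mg/mL are 1, 2 and 3 mL per visit, or two injections of 0.5, 1.0 and 1.5 mL.

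**Reproducing the plan's own figures.** Protocol 9.5: "Participants will be randomized initially in a 1:1:1:1 ratio to all four treatment arms (until approximately 72 participants are randomized"), which gives 72/4 = 18 placebo. Assuming an equal split, that is 6 per volume. The remaining 190 - 18 = 172 join the 300 mg volume: 172 + 6 = 178, and 6 + 6 + 178 = 190. The total is 18 + 18 + 190 + 190 = 416, as stated.

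**Placebo in the A + C pool.** 6 + 65 = 71 at 1 mL, 6 at 2 mL and 178 at 3 mL; total 255.

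| Dose | Active n | Placebo at same volume | Placebo at another volume |
|---|---|---|---|
| 100 mg | 148 | 71 (27.8%) | 184 (72.2%, all larger) |
| 200 mg | 18 | 6 (2.4%) | 249 (97.6%) |
| 300 mg | 190 | 178 (69.8%) | 77 (30.2%, all smaller) |

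The combined ponsegromab column is not matched either: mean volume (148×1 + 18×2 + 190×3)/356 = 2.12 mL, against (71×1 + 6×2 + 178×3)/255 = 2.42 mL for placebo.

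**Possible distortion.** The documents give no ISR rate by volume, so the rates below are assumptions. Let p1, p2, p3 be the placebo rates at 1, 2 and 3 mL. The pooled rate is P = (71·p1 + 6·p2 + 178·p3)/255. With no drug effect, the apparent difference at a dose is its own-volume rate minus P.

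| Assumed p1/p2/p3 | P | 100 mg | 200 mg | 300 mg |
|---|---|---|---|---|
| 5/5/5% | 5.0% | 0 | 0 | 0 |
| 1/1.5/2% | 1.71% | -0.7 | -0.2 | +0.3 |
| 2/4/6% | 4.84% | -2.8 | -0.8 | +1.2 |
| 5/10/15% | 12.1% | -7.1 | -2.1 | +2.9 |

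Differences are in percentage points.

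**Would a Tier 2 risk difference arise?** With 2/4/6% and no drug effect, placebo is expected at 4.84% and combined ponsegromab at (148×2 + 18×4 + 190×6)/356 = 4.24%, both just under the 5% threshold. At lower rates the distortion would appear only in the descriptive table; at 5/10/15% a risk difference would be expected.

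**Precision cost of matching.** Wald 95% half-widths at 2/4/6%, with p the own-volume rate, n the active number and m the matched placebo number: pooled 1.96·√[p(1-p)/n + P(1-P)/255]; matched 1.96·√[p(1-p)(1/n + 1/m)]. Results: 3.5 to 4.0 points at 100 mg, 9.4 to 18.1 at 200 mg, 4.3 to 4.9 at 300 mg.

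**Cohort balance.** Cohort C supplies 130/148 = 88% of the 100 mg group, 65/255 = 25% of pooled placebo and 65/71 = 92% of matched placebo. At 300 mg, active and matched placebo both come entirely from Cohort A. Matching therefore largely restores a within-cohort comparison, which unmodelled adverse event tables otherwise lack.

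**The case against.** The strongest case against is that nothing shows a volume effect. No ISRs were seen in the completed studies (Protocol 2.3.1 and 8.3). Every arm receives two injections. Cohort A and C participants first receive open-label placebo injections at the 300 mg volume and may decline to go on if they do not tolerate them, which plausibly flattens any gradient. The ISR table is descriptive, and SAP 6.2.5.1 treats safety analysis as exploratory and Tier 2 intervals as screening tools. All of this stands; it limits the likely size and makes the direction conditional.

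Three stronger readings might be inferred, and the documents do not support them.

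- *Every dose faces placebo of a different volume.* At 300 mg, 70% of the pool has the same volume. In Cohort A alone, the basis of both interim analyses, it is 178/190 = 94%. In Cohort D, reported separately, it is all of them.
- *The choice between 100 and 300 mg is distorted.* A common placebo cancels: (r300 - P) - (r100 - P) = r300 - r100, where r is the observed rate at a dose. Each dose's own rate is also shown, whatever the placebo grouping.
- *100 mg will look better tolerated than it is.* That requires ISRs to rise with volume, which is an assumption.

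It is also fair that volume is part of what a patient on 300 mg receives. Matched subtraction isolates the drug and removes that burden, so the pooled table answers a legitimate question and should stay.

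**Conclusion.** The point holds as a modest, conditional one. The single placebo group in the A + C safety tables mixes the three volumes as 71/6/178 of 255, and the mismatch is substantial at 100 mg and 200 mg and minor at 300 mg. If ISRs rise with volume, the drug-versus-placebo reading, and any Tier 2 risk difference for an ISR term, would understate an excess at 100 mg and modestly overstate one at 300 mg. Over the assumed rates the distortion runs from zero to about -7 points at 100 mg and +3 points at 300 mg. Given the absence of ISRs in the completed studies, nothing in the documents points to the upper end.

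The counts are planned numbers and assume that the optional Cohort C is enrolled in full. The mL figures are derived from the strength. This is a low-cost improvement to one safety output and does not touch the primary efficacy analysis.

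**What to change.** In SAP 6.2.5.1, keep the pooled ISR table and add a second table of ISR incidence and severity (all-causality and treatment-related) with placebo split by matched volume. Where an ISR term qualifies for a Tier 2 risk difference, also give it against the volume-matched placebo: 100 mg against 71 and 300 mg against 178. At 200 mg, show the 6 matched placebo participants descriptively only. A footnote should state the volume mix of the pooled placebo column.

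The cost is one extra split of an existing table. The assigned volume arm should be available from the randomisation system, and no dose, procedure or data collection changes. The statistical price is the smaller comparator and the wider intervals shown above: small at 100 and 300 mg, and prohibitive at 200 mg, which is why no matched interval is proposed there.

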#### **6.2.5.2. Laboratory Results**

Laboratory data will be listed and summarized by treatment group (including ponesegromab combined) and overall, in accordance with the sponsor reporting standards.

Absolute values and change from baseline at Week 22 in lipid panel endpoints (total cholesterol, HDL-cholesterol, non-HDL-cholesterol, calculated LDL cholesterol and triglycerides) will be summarized by treatment group (including ponesegromab combined) and overall.

### 6.2.5.3. Vital Signs

Absolute values and changes from baseline in vital signs (supine systolic and diastolic blood pressure and pulse rate) will be summarized by treatment group (including ponesegromab combined) and overall, and timepoint, according to sponsor reporting standards.

In addition (except for the PK cohort), changes from baseline will be analyzed using an MMRM model, as described in Section 5.2.3. The MMRM model will be fitted to the change from baseline at all post-treatment timepoints up to Week 22 using the safety analysis set (as defined in Section 4). Additional terms for baseline LVEF, log GDF-15 concentrations from SV1 and baseline log NT-proBNP may be fitted in the model. The Main Cohort (Cohort A) and Cohort C will be reported combined, with data from the same treatment group combined across cohorts; Cohort D will be reported separately. Note that cohort will be included as a term in the statistical model when analysis includes data from more than one cohort.

Maximum increase/decrease from baseline for supine systolic and diastolic blood pressures and maximum increase/decrease from baseline for supine pulse rate will be summarized by treatment group (including ponesegromab combined) and overall, according to sponsor reporting standards.

Maximum absolute values and changes from baseline for supine vital signs will also be summarized descriptively by treatment group (including ponesegromab combined) and overall, using categories as defined in Appendix 5. Numbers and percentages of participants meeting the categorical criteria will be provided. All planned and unplanned post dose timepoints will be counted in these categorical summaries. All values meeting the criteria of potential clinical concern will be listed.

### 6.3. Other Endpoint(s)

Unless otherwise stated these analyses will be performed on the censored analysis sets, as defined in Section 4, using efficacy approaches 1, 3 and 4, as described in Section 5.2, unless otherwise stated.

